3 OBJECTIVES AND ENDPOINTS

OBJECTIVES	ENDPOINTS	JUSTIFICATION FOR ENDPOINTS
Primary		
To compare pathologic apoptotic indices in prostatectomy specimens from patients who undergo immediate prostatectomy versus those treated with cabozantinib followed by prostatectomy.	Apoptotic index by cleaved caspase-3	To evaluate the activity of cabozantinib in prostate tumors by understanding its ability to cause cell death.
Secondary		
To conduct immune phenotypic profiling on the peripheral blood and tumor microenvironment in prostatectomy specimens from patients who undergo immediate prostatectomy versus those treated with cabozantinib prior to prostatectomy.	
Description of immune biomarkers, including:
 
 • Immune phenotyping of paired peripheral blood and tumor tissue: Myeloid-derived suppressor cells (MDSCs), neutrophils, M1 macrophages, and M2 macrophages in tumor tissue • Immunohistochemical (IHC) analysis of CD8+, programmed death ligand-1 (PD-L1), cytotoxic T-lymphocyte-associated protein 4 (CTLA-4), interleukin-1 receptor antagonist (IL-1RA) and B7H3 in tumor tissue • Neutrophil chemotactic factors (CXCL12 and HMGB1) and MDSC-promoting 	To confirm pre-clinical observations, ^{9,10,23} understand the effects of cabozantinib on the immune microenvironment, and evaluate the rationale for combination of cabozantinib with immune checkpoint inhibitor (ICI) therapy.

OBJECTIVES	ENDPOINTS	JUSTIFICATION FOR ENDPOINTS
	cytokines (CCL5, CCL12, CD40) in tumor tissue	
Exploratory		
1. To estimate the pathologic complete response rate (pCR) and \leq pathologic T2 (\leq pT2) rate in each arm.	1. Rates of pCR and \leq pT2	1. To understand the efficacy of cabozantinib as measured by key clinical pathologic endpoints.
2. To evaluate relapse-free survival in each arm.	2. Relapse-free survival rate at 3 years	2. To understand the efficacy of cabozantinib as measured by a key clinical endpoint.
3. To compare apoptosis (TUNEL), proliferation (Ki-67), and microvessel density (CD31) indices in prostatectomy specimens from patients who undergo immediate prostatectomy versus those treated with cabozantinib prior to prostatectomy.	3. Quantification of TUNEL, Ki-67, and CD31 staining	3. To describe the effects of cabozantinib on tumor tissue as measured by other standard pathologic parameters.

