4.2 CORRELATIVE STUDIES

Please see the lab manual for further details of these analyses.

Apoptosis

Cleaved Caspase-3. Caspase-3 is a central downstream executor of both the intrinsic and extrinsic apoptosis pathways, and is responsible for the proteolytic cleavage of key effector molecules such as nuclear poly (ADP-ribose) polymerase (PARP).²⁹ Cleavage of the zymogen form of caspase-3 to its active p17 and p12 fragments by caspase 8,9,10, or 12 is essential for downstream induction of apoptosis. The primary endpoint is comparison of apoptosis in prostatectomy specimens in cabozantinib-treated patients versus controls.

Comprehensive Immune Profiling

We will focus on comprehensive immune profiling of available samples representing the cabozantinib-treated and untreated tumor microenvironment (TE) as well as baseline and longitudinal PBMC samples in cabozantinib-treated and untreated patients in an attempt to identify both: (1) baseline signatures that predict which patients might benefit from cabozantinib, as well as (2) pharmacodynamic signatures that could provide mechanistic insights regarding therapeutic responses. The TE (tissue) will be analyzed in the laboratory of [name] (Duke Chair of Pathology). The profiling platform to be used to analyze the peripheral blood (PBMC) samples will be highly standardized, polychromatic flow cytometry assays that have been developed by the Duke Immune Profiling Core (DIPC; Director: [name]) specifically for monitoring immune signatures in the context of immune checkpoint blockade trials.

Pathologic Response

Complete pathologic response (pCR) is defined as complete resolution of all cancerous glands in the prostatectomy specimen. Patients treated with cabozantinib who have pCR will be defined as *extraordinary responders*. Tissue from these patients' prostate biopsy will be collected for analysis and correlation with key correlative endpoints.

Relapse-free Survival

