The Affymetrix® U133A 2.0 Microarray, or similar, will be used for all analyses. Microarray hybridization and scanning will be performed as previously described.³¹ A k-nn (nearest neighbor) analysis will be performed to identify genes that have their expression most closely associated with cabozantinib administration. Random permutation testing will be used to determine if the number of genes identified as having expression differences associated with cabozantinib administration is greater than would be expected by chance alone. Additional analyses can be performed to determine if particular patterns of gene expression are associated with response to cabozantinib. This analysis can initially be performed using pathologic response to cabozantinib as a dichotomous variable based on pre-established criteria. In this analysis, genes are identified in the control and cabozantinib-treated prostatectomy specimens that are most closely associated with response to cabozantinib using k-nn, similar to the analysis above. Using a similar dichotomous variable analysis, expression patterns will be correlated with VEGF and c-MET, HGF, and phospho-c-MET levels. Finally, we will test genes associated with apoptosis, androgen receptor signaling, c-MET activation,^{32,33} and a c-MET-specific endocytosis panel^{34,35} for correlation with response to cabozantinib. These studies will be performed and analyzed by [name] at the Duke Cancer Institute, Assistant Professor of Medicine and Research Scientist in the Genitourinary Oncology Laboratory. [name] completed a postdoctoral fellowship in the Duke Institute for Genome Sciences and Policy (IGSP) and has experience analyzing gene expression and pathway signatures in human solid tumors.

Mesenchymal Markers

An exploratory endpoint of this study will be to describe changes in mesenchymal markers associated with cabozantinib treatment. We hypothesize that patients treated with cabozantinib will have evidence of mesenchymal markers to a lower degree than controls, indicative of a mesenchymal-epithelial transition (MET).

Intratumoral Androgens

The importance of ongoing steroidogenesis within prostate tumors, despite anorchid serum androgen levels, is now appreciated.³⁶ Two recently reported studies of androgen suppression in the neoadjuvant-to-prostatectomy setting demonstrated that the androgen receptor (AR) axis is still active despite near

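### The optional gene analysis of response to cabozantinib pools untreated controls with treated men and has no arm adjustment, so drug-effect genes can be mistaken for response genes

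*Combined protocol and SAP*

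**What the plan says.** Section 4.2 (Correlative Studies), under Gene Expression Analysis, describes two analyses. The first is a k-nn analysis to "identify genes that have their expression most closely associated with cabozantinib administration", and controls belong there. It has its own check against chance: "Random permutation testing will be used to determine if the number of genes identified as having expression differences associated with cabozantinib administration" is larger than expected by chance.

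The second is optional: "Additional analyses can be performed to determine if particular patterns of gene expression are associated with response to cabozantinib". It may begin by "using pathologic response to cabozantinib as a dichotomous variable based on pre-established criteria", and in it "genes are identified in the control and cabozantinib-treated prostatectomy specimens that are most closely associated with response to cabozantinib using k-nn".

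The protocol does not give those criteria. It does not say which class a control belongs to, limit the second analysis to Arm A, or include an arm term. The permutation test is stated for the first analysis only. Section 4.2 refers to a lab manual for further detail, which is not among the documents.

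The only pathologic response that Section 4.2 defines is pCR: "Complete pathologic response (pCR) is defined as complete resolution of all cancerous glands in the prostatectomy specimen". The responder label there is confined to the treated arm: "Patients treated with cabozantinib who have pCR will be defined as" extraordinary responders. Section 3 (exploratory objective 1) nevertheless estimates pCR and ≤pT2 rates in each arm, and Section 11.1 compares such rates between arms. Section 11.1 also gives 10 control and 20 treated evaluable men, and says gene expression will be reported descriptively.

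**The concern.** Response to cabozantinib can be observed only in a man who took it. Once controls enter the analysis they must be put in some class, and either choice causes trouble.

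- **Classed as non-responders.** Every responder is treated, while the comparison group is a mixture of treated and untreated men. A gene that the drug shifts in every treated man then differs between the classes even if it says nothing about who responds.
- **Classed by their own pathology.** A control with ≤pT2 disease has not responded to anything. His category reflects the disease he came in with, so genes tied to stage are mixed with genes tied to response.

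At stake is the interpretation of a gene list. The same paragraph goes on to test apoptosis, androgen-receptor and c-MET genes for correlation with response, and the drug itself could plausibly alter these pathways.

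**Working it through.** **The plan's own figures.** None is stated for this analysis. As a check on the arm sizes and the SD scale, the primary-endpoint power in Section 11.1 was reproduced. With 10 v 20 men, two-sided 0.05 and 28 df, the noncentrality is d/√(1/10 + 1/20). Power is 70.3% at d = 1.0 and 96.2% at d = 1.5, against the stated 70% and 96%.

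**Inputs.** From the documents: 20 treated men and 10 controls. Assumed, because the plan gives nothing: the number of responders R among the treated, the drug effect s in SD units, and a two-sample t-test at p<0.05 in place of k-nn, whose settings are not stated. Each scenario simulates 20,000 genes that are shifted by s in all treated men and unrelated to response.

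**Controls pooled as non-responders.** Responders have mean shift s. The comparison group has (20 − R) treated men and 10 controls, so its mean shift is s(20 − R)/(30 − R). The spurious difference is

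s − s(20 − R)/(30 − R) = 10s/(30 − R).

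| R | 10s/(30 − R) at s = 1.5 | Called response genes at s = 1 / 1.5 / 2 / 3 |
|---|---|---|
| 2 | 15/28 = 0.54 | 5% / 5% / 4% / 2% |
| 4 | 15/26 = 0.58 | 7% / 9% / 10% / 10% |
| 6 | 15/24 = 0.62 | 11% / 15% / 19% / 25% |
| 10 | 15/20 = 0.75 | 19% / 33% / 47% / 71% |
| 14 | 15/16 = 0.94 | 33% / 60% / 80% / 98% |

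Using treated men only, or both arms with an arm term, the share is 4.6% to 5.3% in every one of these scenarios. The bias in the mean is present even at R = 2, but two responders give too little precision for it to produce extra calls.

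**Controls classed by their own pathology.** With c of 10 controls in the favorable class, the spurious difference is s[R/(R + c) − (20 − R)/(30 − R − c)].

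- Equal rates, 10/20 and 5/10: s(10/15 − 10/15) = 0. The simulated share is 3% or less.
- 14/20 v 4/10: s(14/18 − 6/12) = 0.28s. The share is 8% to 11% over the same range of s, and about 5% with an arm term.

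**Ranking instead of a p-value.** This check assumed 10,000 genes, 500 of them drug-changed by 1.5 SD and 50 true response genes, ranked by signal-to-noise. With controls pooled as non-responders, the top 100 held about 9, 16, 31 and 52 drug-only genes at R = 4, 6, 10 and 14, against 3 to 4 with treated men only. Pooling also placed somewhat more true response genes in the top 100 (36 v 30 at R = 10), so restriction is not free.

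**Which R is plausible.** Section 2.3 expects pCR only in a minority subgroup and gives no rate. For assumed pCR rates of 5% and 10%, the chance of at least 2 pCRs in 20 men is 26% and 61%. Counts near 10 would need a looser criterion, such as ≤pT2.

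**The case against.** The strongest defense is that the documents do not establish the harmful coding. A reader might infer that all 10 controls are counted as non-responders and that drug-changed genes will therefore be reported as response genes. The protocol does not say this. It names the specimens but gives no class for a control, and since pCR and ≤pT2 are estimated in each arm, a control can have his own category. On that reading the inflation may be zero. If response means pCR, responders are probably few and the inflation is small or absent even under pooling. The larger percentages need both the pooled coding and a looser definition of response.

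The analysis is also optional, and its results are to be described rather than tested definitively. The plan states no p<0.05 gene-calling rule. Exploratory objective 10 concerns expression correlated with drug administration, and its stated justification is possible later analysis. A reader might infer that the response genes are meant to steer later combination trials. Section 2.2 supports only a general hypothesis-generating aim for the whole study. Because the administration analysis comes first, overlap between the two gene lists could be inspected.

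All of this limits the size and certainty of the problem. What remains is that the protocol expressly puts untreated men into an analysis of response to the drug, with neither restriction nor arm adjustment. Scoring controls by pathology does not turn their category into drug response. Nor would extending the permutation test help: permuting response labels freely across both arms breaks their link with arm, so drug-effect genes would still look like an excess over chance.

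**Conclusion.** The point holds as a minor one. As written, the response analysis can confound response with exposure. If controls are pooled as non-responders, an assumed 1.5 SD drug effect gives a mislabelling share of about 5% at 2 responders, 9% at 4, 15% at 6 and 33% at 10, against about 5% in treated men only. If controls are classed by pathology, the inflation ranges from none at equal rates to about 8% to 11% at 14/20 v 4/10, and the class still does not measure response to cabozantinib.

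These figures rest on assumed effect sizes and responder counts and on a t-test in place of k-nn. They show direction and range and do not forecast this trial's results. The documents do not support saying that mislabelling is certain. The primary endpoint is not touched.

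**What to change.** In Section 4.2, run the response analysis within the cabozantinib-treated men, or keep both arms with an arm term. Use the controls for the cabozantinib-administration analysis already planned. State the response criteria and, if controls stay in, how they are classed. k-nn takes no covariate, so an arm term means selecting genes with a per-gene linear model; restriction is simpler if k-nn is kept. If controls are classed by pathology, the arm term removes the drug-effect inflation, but the result should be described as association with pathologic category, not response to the drug.

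The cost is a sentence or two. Restriction leaves 20 rather than 30 men, with some loss in finding true response genes; the alternative costs one model term.

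If response means pCR, state as a limitation that responders' prostatectomy tissue holds no tumor, so the contrast is partly benign against malignant tissue. Removing controls does not cure this. Pre-treatment biopsy might seem the remedy, but the Arm A schedule of events retrieves archival biopsy only for men with pCR, if available. Profiling non-responders' biopsies would need retrieval and assays that the plan does not schedule, so it is not proposed here.

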4. To measure expression levels of c-MET, VEGF, and HGF, as well as activation status of c-MET in prostate tissue.	4. Quantification of c-MET, VEGF, HGF, and activated c-MET in prostatectomy tissue	4. To evaluate effects on the c-MET/HGF axis.
5. To describe changes in plasticity signaling markers associated with prostate tumors, including vimentin, AR, SNAIL, AXL, and N-cadherin, with cabozantinib exposure	5. Correlation of changes in vimentin, AR, SNAIL, AXL, and N-cadherin with cabozantinib exposure	5. To describe effects on markers of epithelial-mesenchymal transitions (EMT).
6. To evaluate PTEN and p53 genomic and protein expression status in tumor tissue	6. Measurement of PTEN and p53 genomic and protein expression status in tumor tissue	6. To evaluate whether cabozantinib may be more active in a subset of pTEN/p53-deficient tumors. ¹⁰
7. To demonstrate that cabozantinib is safe and tolerable in patients	7. Adverse events by CTCAE v5.0, dose intensity of cabozantinib.	7. To demonstrate that cabozantinib is safe and tolerable in patients

OBJECTIVES	ENDPOINTS	JUSTIFICATION FOR ENDPOINTS
undergoing radical prostatectomy.		undergoing radical prostatectomy.
8. To demonstrate that surgery is safe and feasible in patients undergoing treatment with cabozantinib.	8. Blood loss at prostatectomy and duration of hospital stay.	8. To demonstrate that surgery is safe and feasible in patients undergoing treatment with cabozantinib.
9. To collect plasma angiome samples (multiplex ELISA) for analysis and correlation with primary and key secondary endpoints.	9. Angiome biomarkers.	9. To collect samples for possible later analysis and correlation with key endpoints
10. To describe gene expression patterns (in particular those associated with apoptosis, androgen receptor signaling, c-MET activation, and a c-MET-specific endocytosis panel) correlated with cabozantinib administration using RNA sequencing analysis.	10. Gene expression patterns.	10. To collect samples for possible later analysis and correlation with key endpoints.
11. To explore changes in serum and intratumoral androgen concentrations related to cabozantinib treatment.	11. Serum and intratumoral androgen concentrations.	11. To collect samples for possible later analysis and correlation with key endpoints.12

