Sample Size Justification. The primary endpoint of this randomized phase II study is the apoptotic index by cleaved caspase-3 in prostatectomy specimens following 4 weeks of treatment with cabozantinib compared with prostatectomy specimens of untreated patients. The target sample size of convenience is 30 patients where the randomization allocation ratio will be 2:1 cabozantinib-to-control. The randomization will not be stratified on any variable. The null hypothesis is that the mean apoptotic indices are equal between the two groups. The percent of tumor cells positive for cleaved caspase 3 staining for each patient will be evaluated for the primary objective. The 6 subjects assigned during the Safety Lead-In Cohort are included in the 30 patient sample size and 2:1 randomization allocation ratio.

Based on data from a prior, unpublished pre-prostatectomy study of sunitinib, we expect the controls to have minimal staining (i.e., $\leq 5\%$). In the proposed study we will enroll 10 controls and 20 cabozantinib-treated patients to demonstrate increased staining (i.e., $>5\%$). A two sample t-test will be used to compare group means. With 10 and 20 evaluable patients in the control and cabozantinib-treated groups, respectively, the test will provide 70% power to detect a mean (for positive tumor cells percentage) difference of one-fold standard deviation based on a two-sided type I error of 0.05; or 96% power to detect an one-and-half fold standard deviation difference. Assuming a 10% unevaluable rate, we will enroll up to 33 patients total to have 30 evaluable patients.

Data Analysis. Box plots and statistical summaries of apoptotic (cleaved caspase-3, TUNEL), proliferation (Ki-67), and MVD (CD31) indices will be presented. In addition, the t-test will be used to compare the two arms on apoptotic index, proliferation and MVD indices. Further, the Chi-square test will be used to compare the two treatment arms on pathologic complete response rate (pCR) and pathologic T2 (pT2) rate. The angiome, gene expression, cell-free DNA and mesenchymal markers analyses will be reported descriptively as the trial's limited sample size will not permit definitive analyses for these exploratory objectives. The t-test will be used to compare the two arms' serum and tissue androgen and androgen precursor levels.

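### Section 4.2 splits tissue VEGF, c-MET, HGF and phospho-c-MET into two classes for the gene-expression correlation, although they are quantified; using the scored scale would be a small, nearly free gain in one exploratory analysis

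*Combined protocol and SAP*

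**What the plan says.** The Gene Expression Analysis text in section 4.2 sets out several steps. Genes associated with cabozantinib administration are found by k-nn, with a permutation check on their number. A further, optional step relates expression to pathologic response: "This analysis can initially be performed using pathologic response to cabozantinib as a dichotomous variable based on pre-established criteria". Next, in firm wording, comes the step at issue: "Using a similar dichotomous variable analysis, expression patterns will be correlated with VEGF and c-MET, HGF, and phospho-c-MET levels". The section closes with tests of named gene panels against response to cabozantinib.

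Section 3 describes the same markers as graded quantities. Exploratory objective 4 is "To measure expression levels of c-MET, VEGF, and HGF, as well as activation status of c-MET in prostate tissue", and its endpoint is "Quantification of c-MET, VEGF, HGF, and activated c-MET in prostatectomy tissue". The synopsis repeats both.

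Section 11.1 names no method for these four markers. It says gene expression will be reported descriptively because the sample is small. For cleaved caspase-3, TUNEL, Ki-67, CD31 and androgen levels it plans t-tests, which use the measured values. Section 4.2 opens by referring to a lab manual, which is not among the documents.

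**The concern.** Pathologic response, as section 4.2 uses it, is a two-class variable. Tissue marker levels generally are not. Applying the response template to them means that two men in the same class count as identical even if their measured levels differ widely. It also means that moving the cut can change which genes rank highest. The documents give no cut-point for any of the four markers and plan no analysis that would avoid one.

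The trial describes itself as hypothesis-generating and has 30 evaluable men, so the likelier failure is to miss a real marker-gene association. What is at stake is the sensitivity of this one side analysis.

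**Working it through.** **Inputs from the documents.** Section 11.1 gives the sample: "With 10 and 20 evaluable patients in the control and cabozantinib-treated groups, respectively", so n = 30, with 20 in Arm A. The only power statement in the plan is for the primary endpoint: "70% power to detect a mean (for positive tumor cells percentage) difference of one-fold standard deviation", "based on a two-sided type I error of 0.05", and 96% at 1.5 SD. No effect size, cut or scoring scale is given for the marker-by-expression analysis, so those are assumptions below.

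**The plan's own figure.** Two-sample t-test, 28 df, noncentrality = d / √(1/10 + 1/20) = d / 0.387.
- d = 1: noncentrality 2.58, power 70.3%.
- d = 1.5: noncentrality 3.87, power 96.2%.

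Both stated figures reproduce. They concern cleaved caspase-3 and are not in question here.

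**Information kept by a split.** Assume a continuous normal marker, linearly associated with expression and cut so that a fraction q lies below. The efficiency relative to the full scale is φ(z_q)² / [q(1 − q)], where φ is the normal density and z_q the normal quantile.
- Median: 0.399² / 0.25 = 0.637. Equivalent sample 30 × 0.637 = 19.1, or 20 × 0.637 = 12.7 within Arm A.
- One-third/two-thirds: 0.595, equivalent to 17.8 of 30.
- 25/75: 0.539, equivalent to 16.2 of 30.
- 20/80: 0.490, equivalent to 14.7 of 30.

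The median is the best-placed cut. There the loss is 1 − 0.637 = 36%, and the correlation is attenuated by √0.637 = 0.80.

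**Sensitivity for a continuous marker.** Simulated bivariate normal pairs, n = 30, two-sided 0.05, arms pooled without adjustment. A two-sample t-test stands in for the two-class comparison. Repeat runs agree to about one point.

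| rho | Spearman | Median split |
|---|---|---|
| 0.1 | 8% | 7% |
| 0.2 | 18% | 14% |
| 0.3 | 34% | 25% |
| 0.4 | 55% | 41% |
| 0.5 | 77% | 60% |
| 0.6 | 92% | 80% |
| 0.7 | 99% | 94% |

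With the 20 men of Arm A alone, rho 0.5 gives 57% against 42%. An upper-quartile cut at n = 30 and rho 0.5 gives 54%.

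The 64% is relative to a fully efficient analysis, and Spearman falls a little short of that. At n = 30 and rho 0.5, Pearson correlation has 83% power, Spearman 77% and the median split 60%.

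**Sensitivity for coarser scores.** Assume three levels holding 50%, 35% and 15% of men, split negative against positive, n = 30, two-sided 0.05. Spearman on the score against the split:
- rho 0.3: 27% against 25%
- rho 0.4: 46% against 42%
- rho 0.5: 66% against 61%
- rho 0.6: 86% against 82%
- rho 0.7: 96% against 94%

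Allowing for simulation error, the gain is about 2 to 6 points. Four equal levels gain more (rho 0.5: 72% against 61%). If a marker is recorded only as positive or negative, both analyses use the same data and the gain is zero.

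**The case against.** The strongest case on the other side is that this is an optional refinement of a minor analysis, and that its size rests on a scale the plan never states. Much of that stands.

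- **Scale.** Objective 4 speaks of levels but also of c-MET activation status, and section 4.2 mentions a double stain without a scoring rule. Any figure for the loss is therefore conditional. A reader might infer that a third of the trial's information is thrown away. The documents do not support that: the 36% needs a continuous normal marker, a linear association and a median split, and it concerns this association only.
- **Objective 10.** A reader might think the split undermines the c-MET part of objective 10. It does not. That objective concerns expression correlated with giving cabozantinib, which has its own k-nn and permutation analysis. The c-MET gene panels are tested against response in a separate sentence.
- **No planned test.** Section 11.1 makes gene expression descriptive, and section 4.2 describes k-nn selection, so no per-gene significance test of marker levels exists. The power figures only index how readily a true association would stand out.
- **Choice of cut.** A reader might infer that the cut will be picked after seeing the data. The lab manual may fix it, and the response analysis that serves as the template refers to criteria set beforehand. A data-driven cut is a possibility, not a finding.
- **Weak associations.** At rho 0.2 or below the gain is under 5 points even for a continuous marker.

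The objection does not remove the mismatch. The plan quantifies the markers, commits to a two-class analysis and offers no alternative. Descriptive reporting does not restore the discarded ordering. A cut fixed in the lab manual would settle how it was chosen but would not recover the lost information.

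**Conclusion.** The point holds for one exploratory side analysis, as an improvement worth making rather than an error that threatens the trial. If the markers are scored on a continuous scale, the split keeps at best about 64% of the information under normality and linearity. The gain in sensitivity at n = 30 and two-sided 0.05 is then about 9 points at rho 0.3 (34 − 25) and 17 points at rho 0.5 (77 − 60). With a three-level score it is about 2 to 6 points, and with a binary status nothing. The correlations are assumed, and the n = 30 figures pool the arms without adjustment, so they illustrate scale and do not predict the adjusted analysis proposed below. The primary endpoint, endpoint 4 itself and the arm comparison in objective 10 are untouched.

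**What to change.** In section 4.2, replace the sentence with:

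> Expression will be related to VEGF, c-MET, HGF and phospho-c-MET on the scale on which each is scored, by Spearman rank correlation adjusted for arm (or within Arm A), with genes ranked by this coefficient and the permutation procedure applied within arm; any high/low split is secondary, with its cut fixed in advance.

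Handling arm matters because section 4.2 treats c-MET, HGF and phospho-c-MET as pharmacodynamic markers. An unadjusted pooled correlation could simply reproduce the difference between treated and untreated men.

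The cost is one sentence and a different statistic inside the same permutation approach, with no new specimens, assays or patients. The small downside is that the output is a correlation ranking in place of a two-class gene signature.
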